## **2 DESCRIPTION OF THE INVESTIGATIONAL PRODUCT**

### **2.1 Overview**

The BioCue™ Kit contains six (6) disposable BioCue™ Separator for the preparation of autologous concentrated bone marrow aspirate (BMAC) at the patient's point of care. The BioCue™ Kit can be used with any legally marketed bone marrow aspiration (BMA) device and associated delivery accessories, provided separately (Table 1). The BioCue™ Kit is used in conjunction with the Biomet Biologics Centrifuge, a table-top swinging bucket centrifuge.

**Table 1. Aspiration Devices and Delivery Accessories Compatible with BioCue™ Kit**

Description	FDA Clearance
H.S. Hospital Service Bone Marrow Biopsy Needle, or equivalent	K013070
Ranfac Bone Marrow Aspiration Needle, or equivalent	501(k) Exempt Product Code GAA
StemCor Systems MarrowMiner Biopsy Instrument, or equivalent	K071732
BD 60 ml Luer Lock Syringe, or equivalent	K980987
BD 30 ml Luer Lock Syringe, or equivalent	K980987
BD 10 ml Luer Lock Syringe, or equivalent	K980987
BD 22 G x 1 1/2 in. hypodermic needle, or equivalent	K021475
Terumo 23 G x 1 1/2 in. hypodermic needle, or equivalent	K771203
Merit Medical 20 ml Luer Lock Syringe, or equivalent	K981417

The BioCue™ Platelet Concentration Kit is indicated for use in the clinical laboratory or intraoperatively at the point of care for the safe and rapid preparation of platelet poor plasma and platelet concentrate (platelet rich plasma, or PRP) from a small sample of blood and bone marrow mixture. The design, materials, and processing methods are identical to the previously cleared GPS® II Platelet Concentration System in BK090008 and to the MarrowStim™ Concentration Kit and MarrowStim™ Mini Concentration Kit in K071934. The BioCue™ Separator is also identical in design to the MarrowStim™ Separators previously utilized in this investigation.

The BioCue™ Separator (**Figure 1**) has a 60 ml capacity and includes a density-tuned dual buoy separation system designed for the isolation and separation of nucleated cells.

**Figure 1. BioCue™ Separator**

The use of the BioCue™ device and Zimmer Biomet Biologics centrifuge to concentrate autologous bone marrow aspirate is illustrated in **Figure 2**. Anticoagulated bone marrow aspirate (60 ml) is loaded into the separator through the center port and covered with the white cap (left picture). The separator is placed into the centrifuge and spun at 3,200 RPM for 15 minutes (center picture). During centrifugation, the marrow's nucleated cells collect between the two buoys within a fixed volume of fluid (6 ml). The red blood cells pack below the bottom buoy and the remaining plasma collects above the top buoy. Following centrifugation, the concentrated bone marrow aspirate (BMAC - right picture) containing the nucleated cells is re-suspended within the fixed volume of fluid. The BMAC is then recovered from the separator by connecting a syringe to the red capped port and extracting the contents.

**Figure 2. Separator (left); Centrifuge (center); BMAC (right)**

The operating specifications for the Zimmer Biomet Biologics centrifuge are provided in **Table 2**.

**Table 2. Operating Specifications for Zimmer Biomet Biologics Centrifuge**

Principle of Operation	Separation based on density of liquids
Table Top	Yes
Refrigerated	No
Swinging Bucket	Yes
Automatic Decanting	No
Micro-Processor Controlled	Yes
User Programmable	Yes, preset program automatically displayed when switched on
Speed Control	Preset, adjustable
Acceleration and Braking	Current-controlled
Maximum RPM	3,500 RPM
Maximum RCF	2,200 g
Tube Capacity	Four 60ml disposable tubes
Imbalance Detector	Yes
Construction	Anti-torsion construction, metal housing and rotor

## **2.2 Proposed Intended Use Statement**

Human bone marrow preparations induce angiogenesis, decrease muscle fiber apoptosis, and stimulate re-epithelialization of wounds in ischemic hindlimb models in mice. Prior to amputation, bone marrow aspirate will be isolated from patients and concentrated using a BioCue™ device (BMAC), thus presenting a more clinically feasible and potent cell population that may improve tissue perfusion and mitigate ischemic wound complications after amputation.

Concentrated, enriched, autologous, bone marrow aspirate is offered as an option to prevent wound complications after amputation. The BioCue™ device is intended for investigational use only to concentrate BMA by selected investigators familiar with their use and experienced in conducting clinical studies. Human BMAC may only be administered IM to human subjects participating in clinical studies sponsored/approved by Indiana University School of Medicine, and who meet all inclusion criteria and have provided formal written consent.

## **3 STUDY OBJECTIVES**

The principal objectives of this study are as follows:

**Determine the safety and explore efficacy of BMAC in preventing wound complications in amputations.** In a Phase I trial, BMAC (up to 5 mL) will be injected into the ATM below the point of amputation in the index limb in an area of approximately 3 x 10 x 3 cm. At the same time, BMAC (1 mL) will be injected at approximately 25 sites in the proximal leg to promote tissue perfusion before

amputation ([Figure 4](#)). Patients will be scheduled for amputation at approximately one week post injection. Safety will be evaluated by review of treatment related Adverse Events during the 12-month follow-up period. Efficacy will be assessed by rates of wound complications and revision of amputation to historical controls at our institution to assess trends in therapeutic efficacy.

**Characterize the host tissue response to, paracrine activity of, and fate of transplanted BMAC.**

Patients will undergo amputation and injection sites at the anterior tibial muscle (ATM) will be harvested at that time. Collection of up to 10 cm of the soleus muscle will serve as control. IHC staining will determine capillary density and local host immune responses. Angiogenic and inflammatory cytokines will be quantified using a multiplex array system and quantitative PCR.

The expected outcomes will provide the framework for the design of a Phase II randomized clinical trial and critical insights that may direct a future trial to test multi-dosing regimens. This investigation will establish a unique clinical model that can expedite safety and mechanistic analyses of projects in PAD that include bioscaffolds to enhance cell survival.

**Determine the effects of chronic limb ischemia and diabetes on nerve function and to assess the effects of mesenchymal stem cell administration on their function.** Peripheral nerve tissue (sciatic, femoral, tibial, sural and/or plantar nerve segments) will be collected at the time of amputation from the amputated portion of the lower limb. Patients with critical limb threatening ischemia, particularly with diabetes, have polyneuropathies that alter motor unit engagement and peripheral sensation leading to ambulatory dysfunction and pressure ulceration of the foot.

## **4 STUDY OVERVIEW**

### **4.1 Study Approach**

This protocol is designed to describe a Phase I single center open label trial study that will enroll up to 12 patients requiring semi-elective amputation within a 30-day period for complications related to CLI.

### **4.2 Study Duration**

It is expected that the study will be completed within 5 years. Each patient will be followed for 52 weeks.

## **5 STUDY POPULATION**

### **5.1 Sample Size and Target Study Population**

#### **5.1.1 Sample size**

The total number of individual subjects is expected to reach approximately twelve (12).

#### **5.1.2 Study population**

The study population will be representative of adults at least 40 years of age who require major amputation, as determined by an independent vascular specialist. It is anticipated that Indiana School of Medicine will enroll up to 12 qualifying adults for this study.

#### **5.1.3 Alignment with intended study population**

The study population includes patients likely to benefit BMAC transplantation.

## 5.2 Recruitment Methods

### 5.2.1 Recruitment for Study

Eligible patients will be invited to participate in the study on a first-come basis, subject to Indiana School of Medicine weekly recruitment goals. They will be informed of the possible risks of the procedure and will be required to give informed consent before study-specific procedures can proceed. A minimal financial inducement will not be offered, and no subject recruitment materials will be used. Each subject will be informed that no personally relevant clinical information will be derived from the collected data. Medications will be documented, and certain medications may be held. Each subject's involvement in the study will be limited to the period between signing of the informed consent form (ICF) and the completion of study specific procedures.

### 5.2.2 Duration of study activities

Enrollment is anticipated to continue for approximately 3 years. In the event that additional studies are going to be conducted, new protocols will be developed specifically for those studies.

## 5.3 Patient Selection

The eligibility criteria for prospective enrollment of subjects are shown in **Table 1**.

**Table 3. Inclusion/Exclusion Criteria for Enrollment of Subjects**

Inclusion criteria	

1. Be <math>\geq 40</math> and <math>\leq 90</math> years of age.

2. Patients requiring lower extremity major amputation, as determined by an independent vascular specialist.

3. If ulceration or gangrene is present, it is distal to malleoli (to allow adequate length of ATM area of approximately 3 cm x 10 cm x 3 cm)

4. Amputation can safely be performed up to 30 days after screening, as determined by an independent vascular or orthopedic surgeon.

5. Females of childbearing potential must be willing to use one form of birth control for the duration of the study. Female participants must undergo a blood or urine pregnancy test at screening.

Exclusion criteria	

1. Patients who are pregnant, planning to become pregnant in the next 12 months, or lactating.

2. CHF hospitalization within the last 1 month prior to enrollment.*

3. Acute coronary syndrome (ACS) in the last 1 month prior to enrollment.*

4. HIV positive or active, untreated HCV as determined by review of medical records.

5. History of cancer within the last 5 years, except basal cell skin carcinoma.

6. Inability to provide written informed consent due to cognitive or language barriers (interpreter permitted).

7. Concurrent enrollment in another clinical investigative trial.

8. Any condition requiring immunosuppressant medications (e.g., for treatment of organ transplants, psoriasis, Crohn's disease, alopecia areata).

9. Presence of any clinical condition that in the opinion of the PI or the sponsor makes the patient not suitable to participate in the trial.

\*As defined by the standard definitions of CHF and ACS by the American Heart Association.

Participant Withdrawal Criteria	At the discretion of the investigator or at the request of the participant.
--	---

## **6 STUDY MATERIALS**

### **6.1 Investigational Product**

#### **6.1.1 Identity of the investigational products**

The BioCue™ Platelet Concentration Device

#### **6.1.2 Safety issues**

Safety of the BioCue™ device to concentrate BMA for the prevention of wound complications in amputation will be determined by review of treatment related adverse events (AE) and serious adverse events (SAE) during the study period of 12 months by the Data Safety Monitoring Board (DMSB) appointed by the Clinical and Translational Sciences Institute (CTSI) at the Indiana School of Medicine or Data Safety Committee (DMC) designated by the Principal Investigator.

The BMAC dose proposed in this trial was selected based on prior clinical trials. We may not see any evidence of efficacy in our composite endpoint, which may reflect an inadequate dose or sample size. In this case we would propose a future study exploring escalating doses of BMAC. In the instance of evolving infection, we would re-assess our inclusion/exclusion criteria and evaluate the contribution of pre-amputation procedures on the lower leg. Patients may request earlier amputation due to worsening rest pain or anxiety. Consideration for amputation sooner than one week post injections will be determined by the PI based on the severity of the subject's condition, so as to offer this research as an option to all eligible subjects.

#### **6.1.3 Handling, storage, accountability**

Autologous heparin-anticoagulated bone marrow aspirate (360 ml) is loaded into 6 Biocue™ separators through their center ports. The separators are placed into the centrifuge and spun at 3,200 RPM for 15 minutes. Following centrifugation, the BMAC containing the nucleated cells is re-suspended within the fixed volume of fluid. The BMAC is then recovered from the separator by connecting a syringe to the red capped port and extracting the contents. All steps (marrow harvest, BioCue™ processing, BMAC administration) are performed at the point-of-care within a single procedure.

Output characterization will be performed on a sample from a single BioCue™ separator chosen randomly. A sample will be pulled from one tube, assuming it is representative of all tubes. The number of cells will be enumerated from one separator and multiplied by six (6). In the case that a positive culture should result from the BioCue™ product, the PI will notify the patient and schedule an examination within 48 hours. The patient will be assessed for evidence of infection including evidence of erythema at the site of the injection, fever (temperature > 100.9 F), and/or leukocytosis (white blood count >11K). In the event of these clinical and laboratory findings, the appropriate antibiotic or antifungal agent will be instituted based on the culture results and recommendations of an Infectious Disease specialist. Follow up examinations and laboratory work will be scheduled based on the severity of symptoms and laboratory findings at the discretion of the PI and per Indiana University School of Medicine procedures.

Sterility testing of the BioCue™ output will be performed in accordance with 21 CFR 610.12. This information will be recorded on a source document and kept in the subject's research chart. Bone

marrow samples remaining after cell characterization may be subject to additional assessments by outside laboratories. Any samples sent outside the site will be identified by subject number only and will not contain any identifying information.

All sterility failures will be reported to the IRB and FDA as adverse events within 30 calendar days. The report will include results of the investigation into the cause of the event and any and all corrective actions taken to mitigate risks to future study subjects.

Following the BioCue™ procedure, laboratory analyses will be performed on unconcentrated and concentrated bone marrow aspirate samples. Total white blood cell (WBC) count, mononuclear cell (MNC) count, mononuclear cell recovery (concentrated MNC/unconcentrated MNC), granulocyte count, platelet count, cell viability, and cell purity (MNC/WBC) will be recorded. In addition, total aspiration volume, total BioCue™ input volume, total BioCue™ output volume, and total delivery volume will be recorded. Additional information, such as CD marker characterization, may also be performed.

#### **6.1.4** Required training

Operating room personnel will be instructed on the use of the BioCue™ Kit and the collection and transfer of bone marrow preparations. The study coordinator will be trained in the operation and management of the centrifugation system.

#### **6.1.5** External studies

No additional studies are planned at this time.

### **6.2** Other Study Materials

#### **6.2.1** Materials to be provided by study site

- Study notebooks to maintain study documents, including signed ICFs, all applicable information, and additional forms to be collected and retained by the study institution during the course of the study.
- Example spreadsheets for tracking patient information.
- Hank's Balanced Salt Solution
- Sodium Heparin

#### **6.2.2** Materials to be provided by device manufacturers

- 1) The BioCue™ Platelet Concentration Device

#### **6.2.3** Materials to be provided by external testing facilities

There are no external testing facilities associated with this study. The cellular characterization work will be performed at the Indiana University School of Medicine core flow cytometry laboratory.

## **7** STUDY PROCEDURES

### **7.1** Workflow

[figure not shown]
The necessity for amputation will be determined by a vascular or orthopedic surgeon not participating in the study. After that decision has been rendered, the patient will be screened for enrollment. After enrollment, 12 patients requiring major amputation for CLI will be scheduled for amputation approximately one week post-BMAC injection in the ATM. Autologous BMA will be retrieved per standard institution procedures. The BioCue™ device will be used per manufacturer instructions.

Patients will receive IM injections of BMAC into the ATM below the point of amputation and up to 25 mL

[figure not shown]
of BMAC in the proximal leg above the point of amputation. Delivery of up to 25 sites of up to 1 mL each of BMAC will be performed in 2 cm increments along the lateral and medial aspects of the upper leg and gastrocnemius to ensure an even distribution. Patients will then undergo amputation approximately one week after injections. Patients will be examined at Baseline, BMAC Injection Day, Day of Amputation, Day 3 post-op amputation, and Weeks 2, 6, 12, 18, and 24 after amputation. At any time during a subject's participation, photographs of current wounds (as applicable at baseline visit) and photographs of the subject's amputation site (at follow-up visits) may be taken to assess wound healing. There will be a week 52 phone call to assess the patient for primary endpoints. Incidence of wound infection, minor (debridement of skin), and major revision (debridement of muscle and bone) of the amputation stump, and revision of amputation will be recorded. Rates of revision of amputation at 12 months will be compared to historical controls. The initiation of treatment will be staggered by a minimum of one week for the first 3 subjects to ensure that potential study treatment-related risks to subjects are minimized.

**Determine the safety and explore efficacy of BMAC in preventing wound complications in amputations.** In a Phase I trial, BMAC (up to 3 mL) will be injected into the ATM below the point of amputation in the index limb. At the same time BMAC (1 mL) will be injected at up to 25 sites in the proximal leg to promote tissue perfusion before amputation (**Figure 3, Figure 4**). Patients will be scheduled for amputation approximately one week post-injections. Safety will be evaluated by review of treatment related AEs during the 12-month follow-up period. Efficacy will be assessed by rates of wound complications and revision of amputation to historical controls at our institution to assess trends in therapeutic efficacy.

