**SYNOPSIS**

Title of Study	Safety and efficacy of concentrated autologous concentrated bone marrow aspirate (BMAC) in preventing wound complications in amputations
Objectives	

• Determine the safety and explore efficacy of BMAC in preventing wound complications in amputations.

• Characterize the host tissue response to, paracrine activity of, and fate of transplanted BMAC.

• Determine the effects of chronic limb ischemia and diabetes on nerve function and to assess the effects of mesenchymal stem cell administration on their function.

Planned Number of Subjects and Duration of Involvement	12 patients, 12 month follow up period
Patient Population	Critical limb ischemia (CLI) patients scheduled for amputation
Investigational Product Name	Concentrated autologous bone marrow aspirate (BMAC)
Methodology Overview	
This is an open label pilot trial.
 
Up to twelve (12) patients scheduled for amputation will receive bone marrow cells concentrated (BMAC) via the BioCue™ Platelet Concentration Kit device injected IM at 25 sites in the leg proximal to the amputation in the index limb to prevent ischemic wound complications after surgery. BMAC will be injected into the anterior tibialis muscle (ATM) below the point of amputation for analytical purposes. Patients will be scheduled for amputation at Day 7 post injection. Safety will be evaluated by review of treatment related adverse events (AE) during the 12-month follow-up period. In subjects undergoing BKA, we will compare rates of wound complications and conversion from BKA to AKA to historical controls at our institution to assess trends in therapeutic efficacy.
 
Patients will undergo amputation and injection sites will be harvested from the ATM at that time. Immunohistochemical staining (IHC) will determine capillary density and local host immune responses. Angiogenic and inflammatory cytokines will be quantified using a multiplex array system and quantitative polymerase chain reaction (PCR).

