**Table 4. Schedule of Events**

Procedures	Baseline Visit 1	BMAC Injection Visit 2	Amp Day Visit 3	Day 3 F/U + 5 days Visit 4	Week 2 F/U +/- 2 days Visit 5	Week 6 F/U +/- 4 days Visit 6	Week 12 F/U +/- 7 days Visit 7	Week 18 F/U +/- 2 weeks Visit 8	Week 24 F/U +/- 2 weeks Visit 9	Week 52 Phone Call
Informed Consent	X									
Medical History	X									
Physical Exam	X	X	X	X	X	X	X	X	X	
Vital Signs	X	X	X	X	X	X	X	X	X	
Con. Medications	X	X	X	X	X	X	X	X	X	
AE/SAE Evaluations		X	X	X	X	X	X	X	X	
Laboratory evaluations	X 				X 	X 	X 	X 	X 	
12 Lead ECG	X				X		X		X	
LEADs / TcPO2	X 				X 	X 	X 	X 	X 	
Photograph of index leg / amputation site	X 				X 	X 	X 	X 	X 	
Schedule Amputation	X									
Research Blood Specimen 		X	X		X	X	X	X	X	
Evaluate for infection, gangrene				X	X	X	X	X	X	X
Evaluate necessity for amputation revision				X	X	X	X	X	X	X
Screening Laboratory Tests: CBC w/diff/plt; CMP (Sodium, Potassium, Chloride, CO2, Glucose, Calcium, BUN, Creatinine); eGFR, hsCRP										
Baseline only: Serum pregnancy testing (childbearing females)										
Follow-up labs: hsCRP										
TcPO2: Transcutaneous Oxygen Pressure; LEADs or Foot TcPO2  will be collected as a baseline measurement, TcPO2 of medial and lateral stump site  will be collected at follow up visits										
Photographs: Index leg at baseline  , BKA stump site at follow up visits  . It is not considered a protocol deviation if photographs were not performed.										
Research blood specimens: Collected prior to induction of surgery (BMAC Injection Day, and Amputation Day) from peripheral vein of up to 30 mL, and at follow-up visits at weeks 2 through week 24. It is not considered a protocol deviation if research blood collection is not performed.										

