**Exploratory Efficacy.** Continuous confidence intervals at the 95% level will be constructed to explore the effect of administration of BMAC on the composite endpoint at 6-months of death, revision of amputation and gangrene, and will be compared to historical cohorts at our institution. The null hypothesis of no change will be rejected if the pairwise confidence intervals does not include zero. The critical levels for the multiplicity adjustment will be determined by simple Monte Carlo simulation.

Quantities over time of BMAC will be fit to an exponential decay curve using a residual pseudo-likelihood procedure and cell half-life ( $\lambda$ ) will be estimated. Binomial confidence Intervals at the 95% confidence level and *p*-values for these four groups after BMAC transplantation will be calculated for the presence or absence of MHC expression and SDF-1 activation. Continuous confidence intervals at the 95% level will be constructed to explore the differences among the time-tiered administration of BMAC for (1) the CD34+CD133+ pro-angiogenic hematopoietic cells recruitment of HIF-1 $\alpha$ /SDF-1/CXCR4 to ischemic muscle, (2) the quantify of capillary density in muscle fibers using hematoxylin phloxin saffron and CD31 counts, (3) VEGF-A,C,D, hepatocyte growth factor, angiopoietin-1 to characterize angiogenic cytokine expression, (4) percent coverage, fiber diameter and cross-sectional area to examine changes in morphology. The correlation between capillary density (CD31 counts) with tissue perfusion (ICA) for each time point will be estimated by Spearman's rank coefficient.

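### Historical comparisons at 6 and 12 months lack a common method of finding events, so differential ascertainment could create or hide a difference, mainly for gangrene

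*Combined protocol and SAP*

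**What the plan says.** **Follow-up of treated subjects.** Section 7.1 schedules examinations on Day 3 "and Weeks 2, 6, 12, 18, and 24 after amputation". Table 4 has a row headed "Evaluate for infection, gangrene" and another for the need for revision. Both are marked at every visit from Day 3 to Week 24 and again at the Week 52 telephone contact. The last examination carries a window: "Week 24 F/U +/- 2 weeks Visit 9". The only scheduled contact after it is the call: "There will be a week 52 phone call to assess the patient for primary endpoints".

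**Comparisons with past patients.** Section 7.1 states: "Rates of revision of amputation at 12 months will be compared to historical controls". Section 9.3 names a "composite endpoint at 6-months of death, revision of amputation and gangrene, and will be compared to historical cohorts at our institution", and says that no change will be rejected if the interval excludes zero. The Synopsis adds a looser comparison without a time point: "In subjects undergoing BKA, we will compare rates of wound complications and conversion from BKA to AKA to historical controls at our institution".

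**What is given about the controls.** The Introduction cites conversion from below-knee to above-knee amputation as high as 19%, drawn from published studies and the institution's own series. No section states the cohort's size, calendar period, data source, event definitions or length of follow-up.

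**Safeguards.** Section 9.2 (Bias Minimization) deals only with order of enrolment. The trial is open label, no adjudication is described, and stump photographs are optional: "It is not considered a protocol deviation if photographs were not performed".

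**The concern.** A comparison with historical controls needs each event to have a similar chance of being found in both groups. Here the treated group has a defined search: repeated examination to Week 24, then one call. The control group's search is undefined, and past patients cannot be assumed to have followed this trial's schedule. Limited stump gangrene may be noted at a scheduled visit and go unrecorded elsewhere. A late revision may be missed if the call fails or is answered incompletely. It may equally be absent from institutional records if it was done at another hospital.

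A confidence interval does not reflect this kind of error, so a reader of the results would not see it. Two features give it weight in an exploratory study: Section 9.3 attaches a rejection rule to the composite, and Section 3 says the outcomes will frame a randomized Phase II trial.

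**Working it through.** The plan states no effect size, power or ascertainment figure for efficacy, so there is nothing of its own to reproduce. The check sets the passages side by side and then gauges the size of the problem.

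**Step 1. How each component can be found**

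| Component | Comparison | Treated subjects | Historical controls |
|---|---|---|---|
| Gangrene | 6-month composite (9.3) | Scheduled examinations to Week 24 | Not stated |
| Revision | 6-month composite (9.3) and 12 months (7.1) | Visits to Week 24, then the Week 52 call | Not stated |
| Death | 6-month composite (9.3) | Visits and call | Not stated |

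Death and operative revision are dated events that records or a direct question can largely capture. Gangrene depends on someone looking at the stump.

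**Step 2. Is there a second source after Week 24?** From Week 24 to Week 52 there are 52 − 24 = 28 weeks without a scheduled visit. Table 4 marks no adverse-event evaluation at Week 52. Section 10.1 says adverse events are not collected or analysed centrally unless serious and judged related to the research. Section 7.1 says revisions will be recorded but names no source beyond the visits and the call.

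**Step 3. Is the window common?** Week 24 ± 2 weeks is 22 × 7 = 154 to 26 × 7 = 182 days after amputation. No day count is set for 6 months in either group.

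**Step 4. Size, as an illustration.** Give both groups the same true rate p and let the proportions of events found be s_B (treated) and s_H (historical). Then:

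spurious difference = p × (s_B − s_H)

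The 19% is from the Introduction. The other rates and all capture proportions are assumptions. With s_B = 100%, the differences in percentage points are:

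| True rate p | s_H = 90% | 80% | 70% | 50% |
|---|---|---|---|---|
| 10% | 1.0 | 2.0 | 3.0 | 5.0 |
| 19% | 1.9 | 3.8 | 5.7 | 9.5 |
| 30% | 3.0 | 6.0 | 9.0 | 15.0 |
| 40% | 4.0 | 8.0 | 12.0 | 20.0 |

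Exchanging the two groups reverses the sign. In 12 subjects, 70% capture in one group corresponds to 12 × 0.057 = 0.68 of an event at 19%, and 12 × 0.12 = 1.44 events at 40%.

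**Step 5. Against random error.** Wilson 95% intervals are 0 to 24.2% for 0/12, 4.7 to 44.8% for 2/12, and 13.8 to 60.9% for 4/12. At 2/12 (16.7%) the interval extends 16.7 − 4.7 = 12.0 points below the estimate and 44.8 − 16.7 = 28.1 above. Most of the tabulated shifts are smaller than that.

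**The case against.** The strongest reply is that this is an exploratory pilot. Section 9.1 says it is not powered for efficacy, the Synopsis speaks of trends, and with 12 subjects chance outweighs most plausible ascertainment shifts. That stands, and it limits the importance of the point. It does not remove it, because the comparison is still planned with a rejection rule.

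Several stronger readings are tempting, and the documents do not support them:

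- **That controls had only routine care.** A reader might infer this, and it is the natural reading. The text says only that they are historical and, mostly, from the institution. What is documented is that their ascertainment is unspecified.
- **That bias runs against treatment at 6 months and in its favour at 12.** Closer examination may raise gangrene counts in treated subjects, but this is only a tendency. At 12 months the comparison names revision alone, a major operation that a patient can report by telephone, including one done elsewhere. Controls known only from institutional records could miss the same kind of event. The sign could go either way.
- **That infection falls under the rejection rule.** Infection is not in the Section 9.3 composite. It could enter only through the general wound-complication comparison, which has no such rule. Likewise, although a call cannot examine a stump, no 12-month comparison names gangrene or infection.
- **That the visit window causes a calculable loss of 6-month events.** The 19% has no stated time horizon, the upper edge of the window reaches 182 days, and deaths and revisions after the last visit can still be learned at Week 52. No figure for this is supportable.

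**Conclusion.** The point holds in a limited form. Treated subjects have a specified method of finding events. Historical controls have none stated, and nothing in Sections 7.1, 9.2 or 9.3 aligns the two. Differential ascertainment can therefore create or hide a difference. Gangrene in the 6-month composite is the main exposure. The risk for revision is smaller and lies in events missed by the call or by institutional records. The direction is not fixed.

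On the illustrative assumptions, the shift is about 2 to 10 points at a true rate of 19% when capture in one group falls to between 90% and 50%, and 12 points at a rate of 40% with 70% capture. The capture proportions and the 40% are assumed, and the documents give no gangrene rate. One event in 12 is 1/12 = 8.3 points, which shows how coarse the rate is but does not measure the bias. This is a cheap improvement worth making, and it does not threaten the study's safety aim.

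**What to change.** In Sections 7.1 and 9.3:

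1. For the historical comparison, take death and operative revision or re-amputation, each with its date, from operative and hospital records. Use the same extraction form and event definitions for treated subjects and controls.
2. Set the same fixed day counts in both groups, for example Day 182 and Day 365, counted from amputation, the starting point both groups share.
3. Use the Week 52 call to prompt the record search, including procedures at other hospitals, and not as the only source.
4. Present the death and revision comparison as the like-for-like result. Report gangrene separately, and infection likewise, with a statement that treated subjects had scheduled examinations.
5. State the historical cohort's data source, calendar period and length of follow-up.

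The cost is some wording and a record review for at most 12 treated subjects; controls have to be extracted in any case for a comparison to be made. The drawback is that gangrene carries less weight in the comparison. Removing it from the composite altogether is a debatable trade-off that this point does not require.
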